The intervention group: In all patients, a balloon occlusion venography of the coronary sinus will be done during the procedure. Supplementary, selective venography may be used to visualise all the CS branches from the CT scan. The local electrical activation is measured and recorded in **all potentially accessible branches of the coronary sinus** (all CS branches, where a LV lead may be positioned), basal, mid-ventricular and apical, and the LV lead is positioned in the CS branch according to the latest local electrical activation, considering acceptable stability, pace threshold and threshold for phrenic nerve stimulation. Guided by the echocardiography, positioning of the LV lead directly in scar tissue is avoided, if possible (see figure 1-3). Mapping is done using the LV lead or/and a guidewire (e.g. Vision wire, Biotronik). Number of mapped CS branches, LV lead target branch, and position in the branch (apical, mid-ventricular or basal) is recorded. The implanting physician will judge, whether mapping can be done using the LV lead, or a supplementary guide wire must be used. Likewise, in each case, the implanting physician will judge the limit for additional operation time and fluoroscopy used for mapping and LV lead placement in each patient.

- In patients with true LBBB mapping is done under the patient's native ventricle activation (LBBB).
- In all other patients the electrical activation in the CS branches is mapped under RV pacing.

In rare cases a very long latency from pacing at the LV lead to start of the generated QRS can be observed. In these cases, where latency exceeds 60-70 ms, and correction for this by programming the VV interval is deemed impossible (and the desired resynchronisation of the contraction therefore not possible), the LV lead is placed according to latest LV activation where this phenomenon is not found.

The control group: In all patients, balloon occlusion venography in the coronary sinus is done during the procedure. Subsequently the LV lead is placed in the branch judged to be most suitable, preferentially in a posterolateral (2-5 o'clock in the mitral annulus), and mid-ventricular or basal, non-apical position, and taking into consideration stability, pace threshold and threshold for phrenic nerve stimulation. Here too, positioning directly in scar tissue is avoided, if possible. Mapping for late activation is not done in this group. See figure 4.

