In both treatment arms: In all patients, fluoroscopic images/film of the position in two planes (LAO 40-60° and RAO 30-40°) of the three leads is recorded and saved by the end of the procedure. Operation time (first

incision - last suture) and fluoroscopy time and dose are recorded. Time used for mapping of CS and positioning of the LV lead is recorded.

After implantation, the VV interval (the interval from pacing in the right ventricle until pacing in the left ventricle) is set for the narrowest possible QRS. The AV interval is set short enough to avoid fusion between the biventricular pacing and the intrinsic ventricular activation.

The day after the implantation, the delay of activation of LV where the LV lead is positioned is measured in all patients (at that time, the lead is expected to be in a stable position that might be a little different from immediately after the implantation). In LBBB patients the interval from RV sensing to LV sensing is measured, in all other patients RV pacing to LV sensing is measured (use device-programmer).

CT scan: In all patients, a contrast-enhanced CT scan for visualisation of the CS branches and later definition of LV scar tissue is done prior to implantation. Moreover, a flash CT scan without contrast is done in all patients after implantation, prior to discharge for a precise determination of the lead positions (14). In patients with significantly reduced renal function (estimated GFR $<30\text{ml/min/1.73 m}^2$) the pre-operative contrast-enhanced CT is omitted, but the post-operative CT without contrast is done.

Randomisation 1:1, stratified for ^atrue LBBB, ^bother BBB and ^cRV pacing (identification of the latest activated LV segment may be especially important in patients without true LBBB). Randomisation is done web-based in the case-record form used for data collection. Block-randomisation is used to ensure that each centre includes a similar number of patients in each treatment group (blocks of 10+10 for LBBB and RV pacing, 5+5 for other BBB). Randomisation takes place after informed consent has been obtained and before device implantation.

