Post implantation, prior to discharge, and in the set device mode (DDD or VVI) ECG-12 with CRT, ECG-12 with pure RV pacing, and ECG-12 with pure LV pacing are recorded. At each follow-up ECG-12 is recorded when the patient arrives, with the existing device settings. The interval from RV pacing to activating the LV lead is measured at each follow-up visit. ECG's are recorded and stored digitally.

At each visit, the patient's current medication is recorded.

Patient-reported outcomes (PRO's):

At baseline and again after 6, 12, 24 and 48 months the following questionnaires will be used:

Kansas City Cardiomyopathy Questionnaire (KCCQ-12), 12 items

Patient Health Questionnaire (PHQ-9), 9 items

Generalized Anxiety Disorder (GAD-7), 7 items

At baseline in addition:

Expectations towards ICD therapy (EXPECT-ICD), 10 items

Brief Illness Perception Questionnaire (BIPQ), 9 items

Resulting in 47 items at baseline and 28 items after 6, 12, 24 and 48 months.

Details regarding PRO's shown in the PRO-appendix.

All patients are followed until the last included patient has been followed for at least 2 years.

If, at 3 months after implantation, there is no clinical response (defined as "*no improvement in NYHA class and <10% improvement of the 6MWT walking distance*") AV and VV optimisation guided by echocardiography is done in both groups. A separate protocol will be prepared for this optimisation.

In patients, who develop or have persistent atrial fibrillation, where sinus rhythm is not immediately obtained by medication and/or by DC cardioversion, there is a risk of a large frequency of intrinsic conducted ventricular activations without effective CRT. If effective CRT drops to <95% the patients are offered ablation of the AV node (His-ablation) or pulmonary vein isolation at the follow-up physician's discretion for the purpose of re-establishing effective CRT close to 100% of the time. If patients develop frequent ventricular extrasystoles that compromise effective CRT (to <95%), ablation for ventricular extrasystoles or medical antiarrhythmic treatment is offered at the follow-up physician's discretion. Atrial fibrillation and ventricular extrasystoles are handled equally in the two treatment arms.

Sample size:

Power calculation:

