- with QLV (time from QRS start to local LV activation where the LV lead is positioned) above/below the median value, respectively
- in NYHA class II and III/outpatient IV, respectively, at baseline
- with baseline LVEF above/below the median value, respectively
- with ischaemic and non-ischaemic background for heart failure, respectively
- with LBBB and non-LBBB, respectively
- with upgrade from RV pacing to CRT and primary implantation of CRT, respectively
- with the RV lead in a septal and non-septal position, respectively (RV lead position determined by flash CT after implantation)

- with the RV lead in an apical and non-apical position, respectively (RV lead position determined by flash CT after implantation)
- with and without echocardiography detected dyssynchrony, respectively (radial time-to-peak, cross-correlation and pattern-analysis) of LV
- scar tissue/perfusion evaluation by CT scan. Total percentage of scar tissue (higher/lower than median) as well as impact of scar tissue localisation with regard to the site of LV lead position (LV lead close to scar (in or in neighbour-segment in a 17-segment model of LV) or remote to scar.

Analysis for statistical interaction is done with respect to the subgroup-analysis above and presented graphically in a Forest plot.

Secondary endpoints are compared in a similar way using Cox regression or multipel linear or logistical regression analysis. In datasets with repeated measures, ANOVA is used. Whether data are normally distributed or not and whether single or repeated data determinations exist are taken into consideration. If relevant, competing risk is adjusted for in the analyses.

A p-value <0.05 is considered significant in two-sided test.

Adjudication of endpoints:

Monthly during the study/follow-up, the study secretariat will verify vital status for all included patients through the Civil Registration System (CPR). In case of death, the centre following the patient will gather information on the death from the patient's GP and from other hospitals/departments, if relevant. This information will be forwarded to the study secretariat coordinating the adjudication of endpoints. A copy of the death certificate is obtained, unless the cause of death is known (e.g. during hospital admission).

The endpoint committee consists of the members of the steering committee.

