In case of true LBBB mapping is done under native activation. In all other patients, mapping of the local electrical activation in the CS branches (Figure 1) is done under RV pacing at a frequency of at least 80/min (must always exceed the patient's native rhythm by at least 10/min). The LV lead or/and an electrically active guidewire (e.g. Vision wire, Biotronik) may be used at the discretion of the implanting physician. The interval in milliseconds from RV sensing (at LBBB and native activation) or pacing to sensing locally in the CS branches is measured using Prucka system or similar ECG recording equipment or device programmer. Measurement proceeds until a vertical, sharp deflection in the electrocardiogram (Figure 2). Measurement is done throughout the course of the vein (basal, mid-ventricular and apical, if possible). The implanting physician will judge the reasonable additional operation time and fluoroscopy used in each patient.

The LV lead is placed with the poles used for pacing corresponding to the latest local activation in the CS branches (Figure 3).

Figure 1

[figure not shown]

Figure 2:

[figure not shown]
[figure not shown]

[figure not shown]
Figure 3

Implantation in the control group:

Preferentially, the LV lead is positioned basal or mid-ventricular (green area in figure 4, left), non-apical, and posterolateral 2-5 o'clock in mitral annulus (indicated in green in figure 4, right).

Figure 4

Example of pre-implantation CT scan showing the CS branches:

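### The QLV subgroup is defined from QRS onset, but no such interval is scheduled; the intervals that are differ by conduction type, and lead-site timing is itself a target of the intervention

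*Combined protocol and SAP*

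**What the plan says.** The subgroup list under Data analysis (Combined protocol and SAP) includes patients "with QLV (time from QRS start to local LV activation where the LV lead is positioned) above/below the median value, respectively". Like the others, this subgroup is to be tested for interaction with treatment on the primary endpoint and shown in a Forest plot.

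The timing measurements that the protocol schedules are these:

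- **Day after implantation, both arms** (Study design, Device implantation): "the delay of activation of LV where the LV lead is positioned is measured in all patients", and the method is "In LBBB patients the interval from RV sensing to LV sensing is measured, in all other patients RV pacing to LV sensing is measured".
- **Mapping during the procedure, intervention arm only** (Implantation in the intervention group): "The interval in milliseconds from RV sensing (at LBBB and native activation) or pacing to sensing locally in the CS branches is measured". For the control arm, the Device implantation text says "Mapping for late activation is not done in this group".
- **Follow-up visits** (Follow-up): "The interval from RV pacing to activating the LV lead is measured at each follow-up visit", with no exception for LBBB. The first visit is at 3 months.

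Randomisation is "stratified for ^atrue LBBB, ^bother BBB and ^cRV pacing". A separate planned subgroup contrasts patients "with LBBB and non-LBBB, respectively". The list of substantial amendments changes none of this.

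**The concern.** The analysis names one variable and the procedures collect others. Every scheduled interval starts at an RV event, sensed or paced; none starts at QRS onset. An analyst given this plan would have to decide, without guidance, which measurement stands in for QLV.

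The only early measurement taken in both arms is also not one quantity. In LBBB it runs from a sensed native RV event; in everyone else it runs from a pacing stimulus, with a different activation wavefront. If the two differ systematically, a single cut puts more of one conduction type in the upper half. The QLV row of the Forest plot then partly repeats the LBBB row under another label.

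A second problem would remain even with a perfect measurement. Activation time at the final lead site is known only after randomisation, and the intervention exists to lengthen it. Lateness of activation is the trial's proposed mechanism, so readers are likely to lean on this subgroup when explaining either a positive or a neutral result.

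**Working it through.** **Definition against measurement**

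| Source | Start point | Who | When |
|---|---|---|---|
| QLV in Data analysis | QRS onset | all, by implication | not stated |
| Day-after check | RV sense (LBBB) or RV pace (others) | both arms | day 1 |
| Mapping | RV sense (true LBBB) or RV pace (others) | intervention arm only | procedure |
| Follow-up visits | RV pace | all | from 3 months |

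No measurement row matches the first. The plan states neither which row supplies QLV nor whether the median is taken over all patients or within stratum.

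**Size of the distortion under a pooled cut**

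The documents give no mean, SD, offset or LBBB share for these intervals, so there is no plan figure to reproduce and every input here is an assumption. Let f be the LBBB share, s the common within-mode SD and d the amount by which the RV-paced interval exceeds the native-sensed one. Both modes are taken as normal.

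1. The pooled median m solves f·Φ(m/s) + (1−f)·Φ((m−d)/s) = 0.5.
2. Shares above m: LBBB a_L = 1 − Φ(m/s); others a_O = 1 − Φ((m−d)/s).
3. Share of patients in a different half than under within-mode medians: f·|0.5 − a_L| + (1−f)·|a_O − 0.5|.
4. Share of variance due to mode: f(1−f)d² / [f(1−f)d² + s²].

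With f = 0.6 and s = 25 ms:

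| d (ms) | m (ms above LBBB mean) | LBBB above m | Others above m | Change half | Variance due to mode |
|---|---|---|---|---|---|
| 0 | 0 | 50% | 50% | 0% | 0% |
| 20 | 7.9 | 38% | 69% | 15% | 13% |
| 35 | 13.4 | 30% | 81% | 24% | 32% |
| 50 | 18.1 | 23% | 90% | 32% | 49% |

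Worked line for d = 35: m/s = 13.41/25 = 0.536, so a_L = 0.296; (13.41 − 35)/25 = −0.864, so a_O = 0.806. Change half = 0.6 × 0.204 + 0.4 × 0.306 = 0.245. Variance share = 0.24 × 1225 / (294 + 625) = 0.32.

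Over a wider grid (f 0.4 to 0.7, s 20 to 40 ms, d 0 to 80 ms) the share changing half runs from 0% to 48%. Mode accounts for half the variance or more only when d ≥ s/√(f(1−f)); at f = 0.6 and s = 25 ms that is 25/0.490 = 51 ms. An offset in the other direction swaps which mode sits high but leaves the share changing half the same.

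**Comparison between arms**

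Because randomisation is stratified by conduction type, f is close to equal in the two arms and the offset cancels in a difference of arm means. Pooling only widens the spread: √(s² + f(1−f)d²) is 26.9, 30.3 and 35.0 ms at d = 20, 35 and 50, against 25 ms within mode.

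**Post-randomisation split**

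In the intervention arm the lead is steered to the latest-activated reachable branch; in the control arm it is preferentially posterolateral and no mapping is done. If the strategy works, some intervention patients are in the upper half who would have been in the lower half under control placement. Those left in the lower half are selected as patients in whom even a targeted site was early, or a late site was not usable. Within either half, the two arms are therefore different kinds of patient.

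**The case against.** - **Pooling is not stated.** This stands. The text refers only to the median value, so a pooled cut is an inference. The supportable statement is that source and cut are unspecified, and that the natural reading mixes two intervals.
- **A reader might infer that the split would sort patients by pacing mode instead of by lateness.** The documents do not support that. They give no distributions, and in the table above mode explains 13% to 49% of the variance at non-zero offsets, with 68% to 85% of patients staying in the same half. Partial contamination is as far as it goes.
- **A reader might also infer that a check of whether the intervention achieved later activation is confounded by conduction type.** It is not, because of the stratification. Pooling costs precision and clarity only.
- **A single-mode interval exists.** The follow-up visits record RV pacing to LV activation without an LBBB exception, so the scales need not be mixed. This stands as a possible source. But the plan does not name it as QLV, it is first scheduled at 3 months, and it does not start at QRS onset.
- **True QLV could be recovered from stored ECGs.** The documents do not establish this. The scheduled post-implant ECGs are under CRT, pure RV pacing and pure LV pacing; no native-rhythm recording is listed, and nothing says LV electrograms are kept for all patients.
- **Limited scope.** This is one of twelve listed subgroup items, and LBBB/non-LBBB is reported separately, so some overlap would be visible. That limits the consequence but does not make the row interpretable.

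**Conclusion.** The point holds in a limited form. On the face of the documents, the QLV used for the subgroup is not scheduled to be measured, and the early interval available in both arms changes its start point with conduction type. Under a pooled median the halves would be partly sorted by measurement mode. The extent is unknown: none at zero offset, about 15% to 32% of patients changing half at offsets of 20 to 50 ms, all conditional on assumed values of SD 25 ms and 60% LBBB.

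The post-randomisation problem needs no such assumptions. It follows from what the intervention does, and standardising the measurement does not remove it. The randomised comparison on the primary endpoint and the sample size are untouched.

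**What to change.** Before unblinding, amend the statistical text as follows.

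1. Replace QLV by the RV-LV interval actually measured, and state which measurement supplies it (day-after or a named follow-up visit).
2. If the day-after value is used, take medians or standardise within measurement mode (native-sensed or RV-paced). Alternatively use one common RV-paced interval, such as that recorded at follow-up, noting that it is first scheduled at 3 months.
3. State which mode applies to LBBB-similar patients: the day-after text says LBBB, whereas the mapping text says true LBBB.
4. Report the interval by arm, within randomisation stratum, as a process measure of whether the intervention achieved later activation at the lead.
5. Remove it from the treatment-effect subgroups, or keep it labelled as non-randomised and exploratory.

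The cost is a few lines of text and a within-mode step in the analysis. No new data are needed. The only loss is the removal or relabelling of one planned Forest-plot row.

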Based on previous studies as well as data from the CRT population at Aarhus University Hospital, Skejby (n=1600) it is assumed that 35% of the population will reach the primary endpoint "death or non-planned hospitalisation for heart failure" within a period of 4 years. Based also on the above mentioned randomised controlled trial of 182 patients and up to 3 years of follow-up, and on the result of the DANISH study, this seems realistic (15). Half of these endpoints are expected to be deaths and the other half of non-planned hospitalisation for heart failure. To show a relative reduction of 25% in the incidence of this endpoint (to an absolute 26%) with $\alpha=0.05$ and $1-\beta=0.80$, n=432 patients must be included in each group. Given these

assumptions, 264 primary endpoints will occur during the study period. Assuming that no more than 10% of the patients withdraw during the study period, it will be sufficient to **include n=500 patients in each group**. Thus, a total of n=1000 patients need to be included in the study. The study is not designed to detect a significant reduction in mortality.

If, alternatively, one wanted to show a 20% reduction (from 35% to 28%), 719 patients should be included in each group (453 primary endpoints), 1500 patients in total. If one wanted to show a 30% reduction (from 35% to 24.5%) 315 patients should be included in each group, 700 in total.

Data analysis:

The primary analysis is carried out as an intention-to-treat analysis (patients randomised to the intervention group are compared with patients randomised to the control group without regard for their actual treatment). The primary data analysis will present time to the primary endpoint in Kaplan-Meier curves for each treatment group and if relevant stratification variable. Hazard ratio for reaching the primary endpoint in the intervention group relative to the control group is calculated by use of Cox regression model. Supplementary, restricted mean survival time is calculated.

Besides a non-adjusted analysis, also an analysis adjusted for age, gender, QRS morphology (LBBB/non-LBBB/RV paced), QRS width (≥ 150 ms / < 150 ms), NYHA class (II/III or outpatient IV), underlying disease (IHD/non-IHD determined heart failure), as well as including centre is done.

Subgroup analyses of the primary endpoint are planned for patients

- with different gender
- with higher and lower age (around the median)

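### Two Cox analyses of the primary endpoint are planned, unadjusted and adjusted, but the plan does not say which one carries the 0.05 decision

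*Combined protocol and SAP*

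**What the plan says.** All of this is in the Combined protocol and SAP.

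- **Allocation** (Study design, randomisation paragraph): 1:1, stratified by true LBBB, other BBB and RV pacing, in blocks of 10+10 or 5+5. "Block-randomisation is used to ensure that each centre includes a similar number of patients in each treatment group".
- **Effect measure** (Data analysis): "Hazard ratio for reaching the primary endpoint in the intervention group relative to the control group is calculated by use of Cox regression model". The sentence names no covariates and no strata. Restricted mean survival time follows and is labelled supplementary.
- **Adjustment** (Data analysis): "Besides a non-adjusted analysis, also an analysis adjusted for age, gender, QRS morphology (LBBB/non-LBBB/RV paced"), then QRS width cut at 150 ms, NYHA class in two groups, ischaemic or non-ischaemic disease, and centre. How centre enters is not stated, nor is the form of age.
- **Decision rule** (end of Data analysis): "A p-value <0.05 is considered significant in two-sided test". It is not tied to either Cox model.

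The list of substantial amendments in the Protocol document shows no change to the analysis.

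**The concern.** A confirmatory trial needs one test that settles the primary question. Here two hazard ratios and two p-values will exist for the same endpoint, and nothing says which one decides if they fall on opposite sides of 0.05.

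The order of the text suggests that the unadjusted model leads. That choice has a cost. Leaving prognostic factors out of a Cox model moves the hazard ratio toward 1 relative to the conditional one, without a matching gain in precision, so power falls. The trial is sized at 80% with little reserve, and the plan already lists the baseline covariates that would recover the loss.

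**Working it through.** **1. The plan's own figure.** Inputs from Sample size: 35% against 26% at 4 years, two-sided alpha 0.05, power 0.80.

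- Uncorrected n = [1.960·√(2·0.305·0.695) + 0.842·√(0.35·0.65 + 0.26·0.74)]² / 0.09² = 410 per group.
- With continuity correction, n = (410/4)·[1 + √(1 + 4/(410·0.09))]² = 432, as stated.
- Events = 432·(0.35 + 0.26) = 263.5, which gives the plan's "264 primary endpoints will occur during the study period".

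No stated figure is wrong.

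**2. Reserve on the hazard-ratio scale.** Under proportional hazards HR = ln(0.74)/ln(0.65) = 0.699. Power = Φ(½·√d·|ln HR| − 1.96); with d = 264 events this is 82.9%. With the unrounded 26.25%, HR = 0.707 and power is 80.5%.

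**3. Simulated power.** The documents give no prognostic strengths, so these are assumptions. Set A: 1000 patients with withdrawal; 5 centres (the budget agrees: 6,000,000 / (200,000 × 6) = 5); strata 55/15/30%; the stated block sizes; follow-up of 2 to 6 years; true conditional HR 0.699; 800 runs per scenario; Monte Carlo error about 1.5 points. Log-hazard settings (stratum HR, covariate SD, centre SD) were 1.3, 0.3, 0.1 (weak); 1.5, 0.6, 0.2 (moderate); 2.0, 0.9, 0.3 (strong). Sets B (2000 runs) and C (1000 runs) used 900 patients, HR 0.70 and the same weak/moderate/strong grading.

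| Power, unadjusted vs adjusted | Weak | Moderate | Strong |
|---|---|---|---|
| Set A | 84 vs 85% | 78 vs 83% | 68 vs 80% |
| Set B | 82 vs 83% | 79 vs 84% | 74 vs 84% |
| Set C | 82 vs 83% | 80 vs 86% | 74 vs 88% |
| Difference, points | 1 | 5 to 6 | 10 to 14 |

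The comparison to read is within a column. In set A the mean event count falls from 281 to 266 to 243 across the columns, which lowers both models' power.

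**4. Hand check of set A.** The formula in step 2 with the simulated events and hazard ratios reproduces the pattern.

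- Moderate: 266 events, unadjusted HR 0.717, gives Φ(2.71 − 1.96) = 77%; conditional HR 0.699 gives Φ(2.92 − 1.96) = 83%.
- Strong: 243 events, HR 0.734, gives Φ(2.41 − 1.96) = 67%; HR 0.699 gives Φ(2.79 − 1.96) = 80%.

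The loss is therefore the attenuation of the hazard ratio.

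**5. Strata alone.** Stratifying set A by stratum and centre without covariates gives 83, 76 and 69%, against 84, 78 and 68% unadjusted. That is no consistent gain.

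**6. Type I error.** In set A under the null, the unadjusted test rejects in 5.0, 4.0 and 3.5% of trials and the adjusted test in 5.4, 4.3 and 4.0%. Neither shows clear inflation.

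**7. Leaving the choice open.** At HR 0.70 the two tests disagree in 2.7, 7.6 and 13.3% of trials in set B, and in 4 to 17% in set C. Under the null, claiming success if either is significant rejects in 6.1, 6.7 and 7.1% (set B, Monte Carlo error about 0.5 points).

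**The case against.** An unadjusted intention-to-treat Cox analysis, supported by a pre-specified adjusted one, is a legitimate design. The adjusted covariate list is closed and includes three-level QRS morphology and centre. The two hazard ratios are different estimands, so the movement toward 1 is non-collapsibility and not an error. The power loss rests on prognostic strengths that the documents do not contain, and if those are weak it is negligible. With the study period extended through 31-12-2026, a change also needs a documented amendment.

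Most of this stands. It rules out a claim that the unadjusted test is invalid, and it means the power loss can only be given as a range. It does not answer the remaining gap: no sentence attaches the 0.05 rule to one model or says what happens if they disagree. The objection that adjustment is only a preference is weak here, because the adjusted model is already planned and needs no new data.

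**Conclusion.** The point holds as a gap in pre-specification with an efficiency cost; validity is not at issue. If the unadjusted model leads, the cost runs from about 1 to 14 points of power. That range depends on the assumed prognostic strengths, stratum shares and follow-up pattern. If the choice stays open, type I error could reach about 7%, and only if either result were accepted as success.

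A reader might infer more than the documents support:

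- **That the trial ignores its strata and covariates.** It does not; the planned adjusted model contains them, and stratification alone adds almost nothing to power.
- **That the unadjusted model is the declared primary analysis.** This is suggested by word order only.
- **That stratified allocation makes the unadjusted test materially conservative.** The simulated null rates of 3.5 to 5.0% show at most a small effect.
- **That restricted mean survival time is a third competing result.** It is already labelled supplementary.
- **That the 150 ms QRS cut is a mistake.** The inclusion criteria make it constant in the other-BBB group, but it still separates patients elsewhere.

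**What to change.** Before unblinding, name one primary analysis in the Data analysis section:

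- a Cox model stratified by the randomisation stratum as randomised (true LBBB, other BBB, RV pacing), which takes over the role of the QRS morphology covariate;
- adjusted for the remaining covariates already listed, with age continuous and the handling of centre stated, for example as a fixed effect;
- the two-sided 0.05 decision resting on its treatment coefficient alone;
- the unadjusted Cox model reported as a sensitivity analysis and restricted mean survival time as supplementary.

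The cost is a short, documented amendment made blind to results by arm. No new data are needed. The reported hazard ratio is then conditional on the covariates, which the report should say. If the unadjusted model is preferred instead, naming it as decisive also closes the gap in the decision rule, at the power cost shown above.
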